In the sorafenib expanded-access programme in the USA and Canada (Stadler *et al.*, 2010) less than 1% of patients achieved CR to treatment with sorafenib in the investigator's opinion.

➤ Retrospective data on real-world studies:

However, in real life this figure may be higher than in a clinical trial setting because the definition of CR is laxer, follow-up of patients is greater and, therefore, the opportunity to reach CR is more feasible, as there are late responders to treatment.

In daily clinical practice, the CT scan is used to assess tumour response, while in clinical trials other additional examinations may be performed, such as a bone scan or brain scans that may reveal metastases that otherwise may not be accounted for.

In the pool analysis of 3 prospective studies published by Castellano (Castellano *et al.*, 2017), 6.1% of patients achieved complete response in the investigators' opinion.

In the **retrospective Spanish SULONG study**, in which 97 patients who had had a PFS to sunitinib greater than 22 months were selected, the percentage of patients who achieved CR reached 21% with a median CR of 33 months (Puente *et al.*, 2017).

In a retrospective series from the hospital Gustave Roussy, [name] analysed 64 patients who obtained CR to TKIs with the drug only (36 cases) or with the combination of local treatment (28 cases); surgery, radiotherapy or radiofrequency ablation (Albiges *et al.*, 2012).

The definition of CR according to RECIST 1.1 criteria was the disappearance of all known target lesions, the disappearance of all non-target lesions and the absence of new lesions.

CR had to be confirmed with two consecutive CT scans performed with at least 4 weeks between them. Confirmation from the oncologist and radiologist was required at each site.

The treatment received was sunitinib in 59 patients and sorafenib in the remaining 5. The dose and regimen used for sunitinib was 50 mg in a 4/2 regimen and sorafenib at 800 mg/24 hours.

Most of the patients had a favourable (22 cases) or intermediate (39 cases) prognosis. However, 3 patients were classified as having a poor prognosis.

Almost all the patients displayed clear cell histology (60 out of 64 patients) and all had been nephrectomised.

There were 26 patients who had a single metastatic location versus 23 who had 2 affected organs and 15 patients who had 3 or more locations.

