The median time to eliminate all lesions from the beginning of TKI treatment exclusively was 12.6 months, with a range of 2 to 28 months.

The median time from CR to relapse was 7.9 months.

In the case of subjects in whom remission of lesions was achieved with TKI plus local treatment, 18.5 months were needed (range of 5-45 months).

The median time from CR to relapse was 8.2 months.

The decision taken regarding whether or not to discontinue the treatment was as follows:

[figure not shown]

Fig 2. Outcome of patients who achieved complete remission (CR) with a tyrosine kinase inhibitor (TKI) alone.

The conclusion of the author was that CR can be obtained in all the prognostic groups and with metastasis in any location.

In the registry-based retrospective analysis of the kidney cancer Czech cooperative group (Buchler *et al.*, 2016) (RENIS registry), which covers 95% of patients treated outside clinical

trials, out of 2,803 patients, 100 cases of CR were identified as the best response (3.6% of the total) obtained exclusively with TKI as a first-line treatment:

- 84 patients treated with sunitinib
- 4 patients treated with pazopanib
- 9 patients treated with sorafenib
- 3 patients treated with bevacizumab + Interferon alpha

96% of patients had been nephrectomised and the same percentage of tumours displayed clear cell histology.

Regarding the MSKCC classification of the prognostic group, 47% of patients had a good prognosis, while 51% had been classified as having an intermediate prognosis and 2% had a poor prognosis.

The response assessment was performed by RECIST 1.1 criteria and an image was only necessary to confirm CR.

The median for achieving CR was 10.1 months and the number of patients with CR increased linearly up to approximately 20 months after beginning treatment with the anti-angiogenic drug.

The patients had a median PFS of 3.8 years (45.6 months) and OS had not been reached in this cohort. The five-year survival rate was 80%.

The decision on whether or not to continue the treatment after the lesions disappeared was shared by the clinician and the patient.

The patients who achieved CR very soon (before 10 months) were more likely to continue with the treatment, while for those in whom the lesions were eliminated later, it was decided to discontinue the treatment in a higher proportion.

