8.5. Sample size

Since this is a case registry with descriptive intent, it is not necessary to make a sample size calculation.

It is planned to include around 90 patients according to an initial estimation, but there is no limit of patients to be included as long as they are circumscribed to the period of case collection. There is no predetermined hypothesis with a defined sample.

The period of case collection will be from the approval of the reference Independent Ethics Committee and opening of the centres until July 31, 2019 or the inclusion in the CRF of all localized cases, whichever occurs first.

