3.2 STATISTICAL DECISION RULES

The statistical significance value is set to $p<0.05$. The SAS statistical software version 9.3 or later (SAS Institute Inc., Cary, NC, USA) will be used.

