4 ANALYSIS POPULATION

4.1 FULL ANALYSIS SET

Since it is an observational and exploratory study, the number of subjects included will not be pre-determined, although a sample of close to 90 cases is envisaged in about 50 Spanish sites; taking the case collection period into account.

Any number of patients that meet the inclusion criteria and no exclusion criteria may be recruited at the site.

Any patient who meets the inclusion criteria and who does not meet any of the exclusion criteria and has received treatment with Sunitinib prior to participation in the registry will be considered evaluable.

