7.2.2. Descriptive analysis

The mean value, standard deviation, median, minimum, maximum, interquartile range (RIQ) and 95% confidence interval (CI 95%) of the following variables will be provided:

- Age of the patients at the start of treatment.
- Pre-treatment necrosis percentage

PFIZER CONFIDENTIAL

[figure not shown]

- Laboratory data at the start of treatment:
 - Haemoglobin
 - Leukocytes
 - Corrected calcium
 - LDH levels
 - Lymphocytes
 - Platelets
 - Neutrophil/Lymphocyte rate
- Time elapsed from the nephrectomy to the start of systemic treatment
- Time on treatment until CR is reached
- Duration of CR
- Time on treatment after CR is reached

The frequency distribution of patients will be presented according to:

[figure not shown]
- ECOG:
 - 0
 - 1
 - 2
 - 3
 - 4
- KPS (Karnofsky Performance Status):
 - 0%
 - 10%
 - 20%
 - 30%
 - 40%
 - 50%
 - 60%
 - 70%
 - 80%
 - 90%
 - 100%
- Motzer prognostic criteria:
 - Favourable (0 factors)
 - Intermediate (1-2 factors)
 - Poor (3 or more factors)
- Heng prognostic criteria:
 - Favourable (0 factors)
 - Intermediate (1-2 factors)
 - Poor (3 or more factors)
- Comorbidities:

PFIZER CONFIDENTIAL

- Cerebrovascular disease
 - Liver disorders
 - Renal failure
 - Autoimmune disease
 - Chronic dermatological disease
 - Obesity
 - Bowel disease
- Metastasis site:
 - Lung
 - Liver
 - Brain
 - Pancreas
 - Nodes
 - Other
- Fuhrman grade:
 - I
 - II
 - III
 - IV
- TNM tumour stage
- Histological type:
 - Clear cell
 - Chromophobe
 - Sarcomatoid, percentage
 - <20%
 - 20-30%
 - 31-50%
 - 51-75%
 - >75%
 - Papillary type 1
 - Papillary type 2
 - Mixed
 - Not performed
- Previous nephrectomy:
 - Yes
 - No
- Complications during surgery:
 - Yes
 - No
- Initial dose and treatment regimen:

PFIZER CONFIDENTIAL

- Sunitinib 50 mg 4/2 regimen
- Sunitinib 50 mg 2/1 regimen
- Sunitinib 37.5 mg 4/2 regimen
- Sunitinib 37.5 mg 2/1 regimen
- Sunitinib 25 mg 4/2 regimen
- Sunitinib 25 mg 2/1 regimen

- Type of treatment received:

- Sunitinib monotherapy
- Sunitinib + subsequent local treatment
- Local treatment techniques for residual lesions:
 - Traditional surgery
 - Radiotherapy
 - SBRT

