- Time on treatment with Sunitinib until complete remission of lesions, calculated as the difference between treatment start date and CR confirmation date (2nd CT scan).
- Duration of complete remission (DOR)
- Progression-free survival (PFS) or time from remission to disease progression, change of treatment due to unacceptable toxicity or death. It will be calculated as the time elapsed from the RC confirmation date (2nd CT scan) until the date of progression/death or change of treatment for unacceptable toxicity, as applicable, or else it will be censored on the date of the last patient follow-up.

Taking into account the asymmetry normally observed in the distribution of survival times and that follow-up periods may be uneven (different study entry date), the Kaplan-Meier method will be used to estimate the median time to CR together with its 95% confidence interval. The median will indicate when complete remission of the disease occurred in 50% of patients.

In order to find associations between time to CR and the baseline features of both patient and tumour, a log-rank test will be used for comparison between groups and the determination of the statistical significance of the correlation between each of the baseline variables and the time to complete remission of disease. The following baseline characteristics are considered:

[figure not shown]
- Demographic characteristics
- Comorbidities
- Tumour data
- Prior nephrectomy in the treatment of metastatic renal cancer
- Classification of the risk group according to Motzer and/or Heng criteria.
- Patient's baseline status, including ECOG grade, presence of anaemia, corrected calcium, LDH levels, neutrophil and platelet levels.

This analysis will establish which baseline characteristics are associated with a shorter complete response time to treatment.

As part of the secondary objectives, the doses and treatment regimens observed in the sample will also be descriptively summarised by means of absolute and relative frequencies. In the case of changes in the treatment dose, the frequency of patients with dose increase, dose reduction and changes in the rest regimen will be specified. Similarly, the most frequent reasons for changes in dosage and/or treatment regimen to RC will be reported.

Frequencies of the type of treatment received will be presented, depending on whether it

Pfizer Confidential

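### SAP 7.2.4 has no small-group rule for its log-rank tests of time to CR; with the sparse groups to be expected for risk group, histology and nephrectomy, the usual chi-square p-values would be too small.

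*SAP*

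**What the plan says.** SAP 7.2.4 states that, to relate baseline features to time to CR, "a log-rank test will be used for comparison between groups". The features listed are demographics, comorbidities, tumour data, prior nephrectomy, Motzer and/or Heng risk group, and baseline status. The section adds that this analysis will determine which characteristics go with a faster CR. SAP 3.2 sets the significance level at 5%. SAP 7.2.4 names Fisher's exact test only for comparing frequency distributions.

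The only category lists are in SAP 7.2.2, which is descriptive. It has three risk groups, nephrectomy yes/no, and under "Histological type" clear cell, chromophobe, sarcomatoid, papillary 1, papillary 2 and mixed, plus a not-performed entry.

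On size, SAP 4.1 notes "although a sample of close to 90 cases is envisaged in about 50 Spanish sites", and Protocol 8.5 says "it is not necessary to make a sample size calculation".

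Protocol 6 describes two series of complete responders:
- Czech registry (100 CRs): "96% of patients had been nephrectomised and the same percentage of tumours displayed clear cell histology". On risk group, 47% were good, 51% intermediate, and "2% had a poor prognosis".
- French single-hospital series (64 CRs): "Almost all the patients displayed clear cell histology (60 out of 64 patients) and all had been nephrectomised". Risk group was favourable in 22, intermediate in 39 and poor in 3.

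**The concern.** The chi-square distribution usually used for the log-rank statistic is a large-sample approximation. It breaks down when one group has only a handful of patients, even if the total is 90. The error is in the harmful direction: p-values come out too small. This differs from multiplicity, because each single p-value is off before the number of tests is considered.

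Risk group, histology and nephrectomy are named factors in the primary objective of seeking associations with CR. The SAP treats the log-rank results as showing which factors matter, and SAP 7.2.4 goes on to a multivariable Cox model meant to support treatment recommendations. A factor could be flagged because of one patient. Take a histology split of 86/1/1/1/1 with three of the singletons at middling ranks. The overall test gives p = 0.003 if the fourth singleton is the 5th of 90 to reach CR, and p = 0.027 if the 7th.

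**Working it through.** The documents give no error rate, power or event number for these tests, so there is no plan figure to reproduce.

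**Step 1. Expected group sizes in 90 cases.**
- Poor risk: 90 × 0.02 = 1.8; 90 × 3/64 = 4.2. About 2-4.
- Non-clear-cell: 90 × 0.04 = 3.6; 90 × 4/64 = 5.6. About 4-6.
- Not nephrectomised: 90 × 0.04 = 3.6; 90 × 0/64 = 0. About 0-4.
- Full risk-group splits: 42/46/2 (Czech shares) and 31/55/4 (French shares: 90 × 22/64 = 30.9, 90 × 39/64 = 54.8, 4.2).

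**Step 2. Events.** Inclusion requires CR as best response, so every patient has the event. There are 90 events and no censoring for time to CR.

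**Step 3. Test statistic.** At each event time j, with Y_j at risk, Y_gj of them in group g, and d_j events:
- U_g = O_g − Σ d_j·Y_gj/Y_j
- V_gh = Σ d_j·[(Y_j − d_j)/(Y_j − 1)]·(Y_gj/Y_j)·(δ_gh − Y_hj/Y_j)
- X² = U′V⁻¹U over k − 1 groups, rejected if above the chi-square 5% point on k − 1 df.

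**Step 4. False-positive rate under the null.** Untied times, 20,000 replicates per split. Monte Carlo standard error near 5% is √(0.05 × 0.95/20,000) = 0.15 percentage points.

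| Factor | Split of 90 | Rejected at nominal 5% |
|---|---|---|
| Simulator check | 45/45 | 5.6% |
| Simulator check | 30/30/30 | 5.8% |
| Risk group | 42/46/2 | 10.8% |
| Risk group | 31/55/4 | 7.8% |
| Nephrectomy | 86/4 | 8.3% |
| Histology, pooled | 86/4 | 8.5% |
| Histology, pooled | 84/6 | 7.3% |
| Histology, separate | 84/3/3 | 12% |
| Histology, separate | 86/2/2 | 15% |
| Histology, separate | 84/2/2/2 | 19% |
| Histology, separate | 86/1/1/1/1 | 37% |
| Histology, separate | 84/2/1/1/1/1 | 39% |

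The extreme of one patient in each of the five non-clear-cell classes (85/1/1/1/1/1) gives 43%.

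**Step 5. Sensitivity.**
- Group sizes drawn at random from the cited shares: risk group 11.2% and 8.2%; histology in six classes 23-27%.
- Times grouped into 2-3-month intervals (median 11 months assumed; the Czech registry reports 10.1): risk group 6.9-9.6%, nephrectomy 86/4 7.2-7.4%, histology 13-26% for the fixed splits tried.
- Histology with random counts and grouped times: 22-24% (1-month intervals), 19% (2-month intervals).

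**Step 6. Permutation reference.** Replacing the chi-square cut-off with the permutation distribution of the same statistic:

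| Split | Chi-square cut-off | Permutation cut-off | Size after change |
|---|---|---|---|
| 42/46/2 | 5.99 | 9.5 | 4.7% |
| 31/55/4 | 5.99 | 7.4 | 5.0% |
| 86/4 | 3.84 | 5.0 | 5.3% |
| 86/1/1/1/1 | 9.49 | about 57 | 4.9% |
| 84/2/1/1/1/1 | 11.07 | about 58 | 5.4% |

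Pooling poor with intermediate gives 42/48 (46 + 2) or 31/59 (55 + 4). Near-balanced two-group splits such as 45/45 and 35/55 run at 5.6%, so pooling alone largely settles risk group.

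**The case against.** **The histology figure.** A reader might infer that the histology test will have a 23-40% false-positive rate. The documents do not support that. The subtype list in SAP 7.2.2 is for frequency tables, and 7.2.4 says only that tumour data are considered. Nothing says how the 4-6 non-clear-cell patients would divide, and the high figures need one or two patients per class and nearly untied times. This objection stands, so the histology figure must be given as conditional.

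**Projected sizes.** The counts come from other cohorts, which include other drugs, and 90 is itself an estimate. Exact 95% limits scaled to 90 run from about 0-6 (2/100) to 1-12 (3/64) for poor risk, and from about 1-9 (4/100) to 2-14 (4/64) for non-clear-cell. Only the smallest group is tiny; it is compared with a large one. With no non-nephrectomised patients there is no test and no error rate. All of this stands, but a pre-specified rule is needed because the counts are unknown.

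**The chi-square reference is not SAP text.** True. It is the usual software default, and the SAP's silence leaves it in place.

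**Exploratory status.** No hypothesis is set, time to CR is labelled a secondary objective in SAP 5.4, and no decision depends on one p-value. This lowers the severity. It does not remove the point, since the SAP sets a 5% threshold and claims to identify associated factors.

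**Another rank test is available.** SAP 7.2.4 also lists Kruskal-Wallis. On uncensored time to CR, its chi-square version rejects 3.6% (42/46/2), 4.9% (31/55/4) and under 1% (86/1/1/1/1) of the time under the null. It is therefore not inflated, but it is not the test the SAP names for this question.

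**Conclusion.** The point holds and should be fixed before the analysis; it is not critical. If the registry resembles the cited series, and the log-rank statistic is referred to chi-square with untied times, nominal 5% tests run at about 8-11% for three risk groups (roughly 1.6 to 2.2 times nominal: 7.8/5 and 10.8/5) and about 8% for nephrectomy at 86/4. Histology runs at about 7-8% if pooled as clear versus non-clear cell. If subtypes are tested separately the rate is about 12-40%, depending on an assumed split; tied times lower it, to about 13-26% for the fixed splits tried. Every sparse split checked exceeded 5%, so the direction does not depend on the assumptions, but the size does.

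A reader might also take this to mean that the primary analysis fails. It does not: the description of complete responses is unaffected, and only the p-values for sparse factors are.

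**What to change.** In SAP 7.2.4:
1. Test risk group as favourable versus intermediate/poor, and histology as clear cell versus non-clear cell. Keep the finer categories for description.
2. Take the log-rank p-value from the permutation (exact) distribution whenever any tested group has fewer than 10 patients. Because time to CR has no censoring, patients are exchangeable under the null and the method applies directly.
3. Report a factor descriptively only when its smaller group is too small to test at all, for example 0-1 patients. Nephrectomy may fall here.

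A blanket ban on testing below 10 patients is not advised. With 4-6 non-clear-cell patients expected it would cancel the histology test in item 1, and it would leave item 2 with nothing to act on. The permutation reference already restores the size. The threshold of 10 only triggers that method and is a matter of judgement.

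Cost: a few lines of SAP text, a little programming and no extra data. Intermediate and poor risk are no longer tested separately, a comparison that 2-4 poor-risk patients could hardly support.

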8. METHODS OF INVESTIGATION

The purpose of this study is to describe in the routine practice setting, outside the clinical trial setting, the clinical characteristics of Spanish patients with metastatic renal cell cancer who have been receiving treatment with Sunitinib since it was marketed in 2007 until 30 October 2018, obtaining CR to treatment on their tumour documented with at least 2 imaging tests.

No hypothesis has been pre-specified, and all the study data will be analysed using descriptive statistical techniques.

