3 HYPOTHESIS TESTING

3.1 STATISTICAL HYPOTHESES

This being an observational and exploratory study, no hypothesis has been established.

PFIZER CONFIDENTIAL

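### A screen of about 16 to 28 unadjusted log-rank tests at p<0.05 is said to establish associations with time to complete response, in a study declared exploratory and hypothesis-free

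*SAP*

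**What the plan says.** Protocol section 8 describes a purely descriptive exercise: "No hypothesis has been pre-specified, and all the study data will be analysed using descriptive statistical techniques". SAP 3.1 agrees: "This being an observational and exploratory study, no hypothesis has been established".

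SAP 3.2 then gives a decision rule: "The statistical significance value is set to" p<0.05. It does not state whether tests are one- or two-sided.

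SAP 7.2.4 uses that threshold. Log-rank tests serve for the "determination of the statistical significance of the correlation between each of the baseline variables and the time to complete remission of disease". The variables are demographics, comorbidities, tumour data, prior nephrectomy, Motzer and/or Heng risk group, and baseline status (ECOG, anaemia, corrected calcium, LDH, neutrophils, platelets). The paragraph ends: "This analysis will establish which baseline characteristics are associated with a shorter complete response time to treatment".

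The same section also plans bivariate comparisons (t test, ANOVA, Mann-Whitney, Kruskal-Wallis, chi-squared, Fisher) and a multivariable Cox regression. It calls the factors predictive of response and says the resulting information will allow treatment-strategy recommendations to be written. Neither document limits the number of tests, orders them, adjusts for multiplicity, or says that p-values only generate hypotheses.

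**The concern.** An exploratory registry may look at many variables, and need not control the family-wise error rate when it does. The difficulty here is the combination: a fixed threshold presented as a decision rule, one test per variable over a long list, no caveat on the p-values, and a promise that the result is established. Read literally, any variable with p<0.05 becomes an established association.

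Looking for associations with baseline characteristics is one of the protocol's primary objectives (section 7.1), so these results are likely to be prominent. With about 90 patients expected and no sample size calculation, a chance finding could be reported as a real feature of patients who respond sooner.

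**Working it through.** Neither document states a number of tests or an overall error rate, so there is no planned figure to reproduce.

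**1. Count the log-rank tests.** SAP 7.2.4 names groups of variables for the log-rank screen. The contents of each group come from the fuller list earlier in 7.2.4, and the metastatic sites from 7.2.2.

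| Group | Grouped | Fully separate |
|---|---|---|
| Age | 1 | 1 |
| Comorbidities (seven listed) | 1 | 7 |
| Tumour: number of metastases, site, histology, Fuhrman grade, necrosis (six sites listed) | 5 | 10 |
| Prior nephrectomy, and time from nephrectomy | 1 | 2 |
| Motzer, Heng | 2 | 2 |
| ECOG, anaemia, calcium, LDH, neutrophils, platelets | 6 | 6 |
| Total | 16 | 28 |

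Intermediate counts:
- Separating comorbidities only: 16 - 1 + 7 = 22.
- Also separating sites: 22 - 1 + 6 = 27.
- Adding time from nephrectomy: 28. That variable is in the fuller list but is not written out in the log-rank list.

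The bivariate tests and Cox models are not counted.

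**2. Chance of at least one p<0.05 when no variable is associated, tests independent.** Formula: 1 - 0.95^m.
- m = 16: 1 - 0.95^16 = 0.560
- m = 20: 1 - 0.95^20 = 0.642
- m = 22: 1 - 0.95^22 = 0.676
- m = 28: 1 - 0.95^28 = 0.762

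The figure first passes one half at m = 14 (0.512).

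**3. Expected number of false positives.** 0.05 × m gives 0.05 × 16 = 0.8 and 0.05 × 28 = 1.4. This does not depend on independence.

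**4. Allow for correlation.** Motzer and Heng share several components, and some of those components are tested again singly. Two-sided z tests with a common correlation were simulated; the correlations are assumed, since the documents give none.

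| m | correlation 0 | 0.3 | 0.5 |
|---|---|---|---|
| 16 | 56% | 48% | 37% |
| 20 | 64% | 54% | 42% |
| 22 | 68% | 57% | 44% |
| 28 | 76% | 64% | 49% |

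One effect works the other way. In a patient-level simulation with 90 patients and no censoring, the figures were 63%, 76% and 84% for 16, 22 and 28 tests, because the large-sample log-rank p-value is somewhat liberal in small groups. The prevalences in that simulation were assumed, so the conclusion does not rest on it.

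**5. Size of a conventional correction, for scale.** Bonferroni would require p < 0.05/16 = 0.0031 or p < 0.05/28 = 0.0018.

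**The case against.** The best defence is that the study is openly exploratory, so unadjusted p-values are normal and readers will discount them. Part of what is needed is also already planned: SAP 7.2.4 gives 95% CIs for Kaplan-Meier medians and quartiles, and hazard ratios with 95% CIs from the Cox model. The first argument would succeed if the SAP carried that caveat, but it does not, and its wording points the other way. The second helps only in part. The hazard ratios are conditional on proportional hazards, and the Cox model adjusts for covariates rather than for the number of tests.

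Four stronger readings are tempting, and the documents do not support them.

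- **That the SAP needed a protocol amendment.** Protocol 8.7 lets the SAP modify the planned analyses and requires an amendment only for major changes to the primary objective or its analysis. Seeking associations is already a protocol objective, and SAP 7.2.4 places time to CR among the secondary outcomes. The empty amendment table belongs to version 1.0 and shows nothing either way.
- **That a false finding is likely whatever the circumstances.** The percentages assume that no variable is associated. With 20 to 28 tests at correlation 0.5, they fall just below one half.
- **That the SAP commits to a particular number of tests.** It names groups of variables. The range of 16 to 28 is a reading of its lists.
- **That a log-rank p<0.05 feeds directly into the treatment recommendations.** SAP 2.2 and 5.1 base these on the strategy used in patients with the greatest benefit, and in 7.2.4 the sentence on recommendations follows the Cox estimates. A direct route from the screen is an inference. The text does not exclude it either.

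**Conclusion.** The concern holds as an overclaim by a stated rule. The documents declare no hypothesis, yet the SAP sets a significance threshold as a decision rule and says that variable-by-variable testing will establish associations, with no multiplicity control and no statement that p-values are nominal.

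If no variable is associated with time to CR, the rule gives at least one p<0.05 with probability about 56% to 76% for 16 to 28 independent tests. For 20 to 28 tests this becomes about 54% to 64% at a common correlation of 0.3 and about 42% to 49% at 0.5. Even the lowest simulated value, 37% (16 tests, correlation 0.5), is about seven times the nominal 5%. The expected number of false positives is 0.8 to 1.4. True associations would reduce the number of null tests and so lower these figures.

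Formal family-wise control is not required in this study. What needs to change is the strength of the claim and the completeness of the reporting.

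**What to change.** - **SAP 7.2.4:** say that the log-rank analysis *will explore*, in place of *will establish*, which baseline characteristics are associated with a shorter time to CR.
- **SAP 3.2:** state that p-values are nominal and hypothesis-generating, and that p<0.05 is not a decision rule.
- **Reporting:** list every variable tested, whatever its result, with effect estimate, 95% CI, raw p-value and Benjamini-Hochberg p-value, and give the number of tests. Fix beforehand how comorbidities and sites are grouped, so that this number is known.
- **Interpretation:** state that no association is presented as established, or carried into the recommendations, on an unadjusted p<0.05 alone.

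The cost is a more modest claim, some wording and one extra table column. No new data are needed and no planned analysis is lost.
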